Severe obesity affects 4.5 million children and adolescents in the US and is rising across all age groups. Adolescent severe obesity is associated with significantly increased risks of cardiometabolic disease, decreased quality of life, and premature death. The most effective and durable treatment for severe obesity is bariatric surgery. However, large prospective trials among US adolescents demonstrate that even after bariatric surgery, more than 50% will remain severely obese at 3 or more vears postoperatively, 8 despite multidisciplinary lifestyle-based postoperative standard of care. To date, there have been very few pre- or postoperative factors identified among adolescents that predict long-term success after bariatric surgery. And, neither preoperative nor postoperative lifestyle-based interventions in adults have had a clinically meaningful impact on long-term weight outcomes.

Bariatric surgery is increasingly recognized as an effective and safe tool to treat adolescents with severe obesity. Current indications for bariatric surgery in adolescents are either 1) A BMI \geq 35kg/m² or \geq 120% of the 95th percentile + an obesity-related comorbidity *or* 2) BMI \geq 40kg/m² or \geq 140% of the

95th percentile alone, *and* a demonstrated ability to adhere to pre- and postoperative recommendations.¹³ Maximal weight loss after bariatric surgery in adolescents is typically seen at 1 year (with the most rapid loss within the first 6 months) followed by modest weight regain. In US adolescent cohorts, weight loss at 6 months after surgery closely approximates weight loss achieved at 3 years.⁷ Notably, in two large observational trials of US adolescents with severe obesity undergoing bariatric surgery, 55-63% remained severely obese at long-term follow-up.^{7,8}

This represents a combination of individuals who did not achieve optimal post-surgical weight loss, who experienced significant weight regain, and/or whose preoperative BMI was so high that even after expected weight loss they remained severely obese. This suggests that bariatric surgery alone will not be the absolute treatment solution for a significant subset of adolescents. These individuals will continue to have unacceptably high personal health risks throughout adulthood, and will pose an ongoing economic and public health burden to society. Interventions that result in even a 1% decrease in obesity prevalence could save an estimated \$4 billion/year in medical costs alone.

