Fourteen patients (7/arm) followed in the Children's Hospital Colorado Bariatric Surgery Center who meet inclusion criteria: 12-24yo; s/p SG or RYGB; and at 6-12 months post bariatric surgery^a, have either a) not achieved mean expected weight loss based on national standards and still have at least class 1 obesity or b) remain severely obese (\geq 120% of 95%ile or BMI \geq 35kg/m2 for 12-17yo; BMI \geq 35kg/m2 for 18-24yo) will be randomized 1:1 to pharmacotherapy + SOC^b or placebo + SOC in double-blind fashion. Expected weight loss at 6, 9, and 12 months postoperatively will be defined as a \geq 26%, \geq 28%, and \geq 31% decrease in weight, respectively, from preoperative weight (within 1 week of surgery) as was observed in the Teen-LABS study.⁷

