(†) All topiramate and phentermine doses will be taken once daily in the morning. Per detailed discussion with pharmacy, once daily dosing of 100mg per day immediate release topiramate is expected to be effective and safe in adolescents, and thus does not require BID dosing.

We chose to intervene at 6-12 months postoperatively because the first year after surgery represents the most rapid phase of weight loss, and interventions that can prolong this most rapid phase may result in improved long-term weight loss outcomes. We are not intervening earlier because there is a gradual dietary progression followed through the first 3 months after surgery and we want participants to be following this stable "lifelong nutrition plan" for at least 3 months before introducing medications that can further alter hunger and satiety.

Standard of care will be delivered throughout the study via the Children's Colorado Bariatric Surgery Clinic's multidisciplinary team, which targets nutrition, physical activity, and self-monitoring. This includes routine in-person clinic visits at 6, 9, and 12 months postoperatively.

Concomitant Medications

Background concomitant medications may be adjusted during the treatment period. Any modifications will be recorded at each study visit within the Concomitant Medication Form. Antihypertensives may be adjusted during the treatment period by the study team. In our experience, some patients who have significant weight loss on phentermine/topiramate, may have a decrease in blood pressure, necessitating a reduction in anti-hypertensive medication dose. Psychiatric medications may be altered by the participant's primary psychiatric prescriber.

D. Description, Risks and Justification of Procedures and Data Collection Tools:

1) Study medications

Overall, we contend that for adolescents and young adults who have undergone the most effective and durable treatment available (bariatric surgery) for severe obesity, and *remain* at high risk for future obesity-related morbidity and premature mortality, the potential benefits of a 12-week trial of phentermine + topiramate outweigh the potential risks.

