 - For routine clinical care, all bariatric surgery patients undergo venipuncture for lab monitoring at 6, 9, and 12 months postoperatively. Study-specific labs will be added to these routine blood draws. The additional study-specific blood tests are needed to detect any changes (between intervention and control groups) in lipids, ALT, and/or hemoglobin A1c as a result of the medication. A pediatric CTRC research nurse will be scheduled to obtain labs at study visit 2, and at Enrollment and study visit 4 if not obtained by the clinical lab. The risks of a venipuncture include pain at the puncture site, possible bruising and edema around the puncture site, less commonly dizziness/presycope/syncope, and rarely infection.
 - DEXA scans will be performed at Visits 1 and 4 (of the total body, hip, and spine).
 The cumulative radiation exposure from these tests is considered small and is not likely to adversely affect participants. The potential risks related to the additive effect of radiation over a lifetime is included in the assent/consent.
 - Indirect calorimetry will be performed at Visits 1 and 4, and uses a canopy method.
 Potential risks include a feeling of claustrophobia, which are included in the assent/consent.
- Optional banking of specimens for future research: This is an optional procedure. For those who assent/consent, blood and urine samples will be collected at Enrollment, Visit 2, and Visit 4. DNA will be isolated from a portion of the whole blood collected at the Enrollment visit only in [name] lab at the University of Colorado Skaggs School of Pharmacy after all samples are collected. Prior to DNA isolation, the samples will be stored at -80°C. The isolated DNA will be stored at -20°C. All other blood and urine specimen, will be processed, fractionated (as appropriate), aliquoted and stored at -80°C.

3) Research-specific study visits

- Patients in the Bariatric Surgery program at Children's Colorado have several standard postoperative visits in the first year after surgery including at 3, 6, 9, and 12 months. The screening/enrollment visit will take place concurrent with the 6, 9, or 12 month postop visit whenever possible. For those with a screening/enrollment visit at 6 or 9 months, Visit 4 will typically take place concurrent with the 9 or 12 month postop visit, respectively. For those with a screening/enrollment visit at 12 months, Visit 4 will typically not be concurrent with a regularly scheduled postop visit.

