- There will be a screening visit at 6, 9, or 12 months postoperatively. Eligible participants will be consented at this visit, and will be asked to come to campus ~1 week later for study visit 1. Enrollment and Visit 1 cannot be combined because it is unrealistic to screen, consent, randomize, obtain study drug, and complete additional measures after an already lengthy clinical appointment.
- The Children's Hospital Colorado Lifestyle Medicine weight management program's clinical protocols for anti-obesity pharmacotherapy require monthly clinic visits for the first three months after initiation for monitoring of effects and side effects. The proposed study protocol follows this standard.

Data Collection Tools (See Table 3. below for Schedule of Measures)

- a) Sociodemographic characteristics: age, sex, race/ethnicity, insurance, highest level of primary caregiver's education, household size and income, government-based assistance, and presence/absence of food insecurity will be obtained from the medical record and the Demographics Form.
- b) Feasibility of protocol implementation: rates of recruitment, enrollment, randomization, and dropout
- c) Study medication adherence & tolerability: assessed by 1) Questionnaire: description/dose/start date of medications, missed doses, and checklists of: effects, adverse effects, and evidence-based barriers to adherence^{51,52}; 2) Pill counts; 3) Urine amphetamine screen
- d) Self-reported changes to all non-study medications: name/dose, interim changes
- e) Patient/family satisfaction questionnaire will assess: reasons for participation, experience during study visits, satisfaction with the effect of the study medication/placebo, ease of communication with study staff, and time burden/inconvenience
- f) Biological outcome and safety measures: Weight, height, heart rate (HR), BP, basic metabolic panel, lipids, ALT, HbA1c, and pregnancy test
- g) Optional Biobanking: Gold top (serum-3.5mL blood), Purple top (EDTA-4mL whole blood), Green top (heparinized plasma-4mL blood), and Urine (volume that remains after the urine pregnancy test for females and a separate urine collection for males) will be collected with participant assent/consent for future research questions.
- h) 3-day dietary record: Participants will complete a dietary record on 3 consecutive days (2 weekday, 1 weekend day) based on standardized protocols for dietary assessment.⁵³

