Planned analyses: Descriptive statistics will characterize the study population. Independent samples t-tests will be performed for continuous variables and chi-square for categorical variables to determine statistically significant differences between experimental and control groups. Aim 1: Feasibility of acceptability (adherence, tolerability, and satisfaction) will be descriptively assessed using differences in proportions between experimental and control groups. Feasibility of protocol implementation will be established by determining the proportions (rates) of recruitment, enrollment, randomization, and dropout. Aims 2,3: Estimated means and variability of continuous health outcome variables (e.g. % change in weight) and intra- and intersubject variability of repeated measures (e.g. loss of control eating) will be graphically presented and visually compared for experimental vs. control groups, as this aim is not powered to run inferential statistics.

G. Summarize Knowledge to be Gained:

The goal of this study is to establish the feasibility and initial efficacy of two common anti-obesity medications for adolescents who require additional risk reduction following bariatric surgery.

Adolescents with severe obesity who don't achieve optimal weight loss and co-morbidity improvement after bariatric surgery have few evidence-based treatment options to mitigate significant health risks through the remainder of adulthood. This study has the potential for substantial impact regardless of results, given that anti-obesity medications are currently being used in the post bariatric surgery setting without an evidence base. A recent international pediatric obesity webinar (4/2019) with contributors from leading adolescent bariatric surgery centers strongly expressed need and enthusiasm for studying the role of pharmacotherapy after surgery. Our center's volume, interdisciplinary expertise, and existing IND to study these medications in this setting sets us apart as the best positioned adolescent bariatric surgery center to carry out this initial pilot, with high potential for a subsequent larger multi-site RCT to evaluate safety and efficacy, mechanism of action, and predictors of response.

H. References:

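### Expected 12-week weight change without drug differs between entry at 6, 9 and 12 months after surgery, but neither the readable allocation text nor the weight comparison takes entry time into account

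*Combined protocol and SAP*

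**What the plan says.** Section IV.D, Research-specific study visits, sets the entry times: "There will be a screening visit at 6, 9, or 12 months postoperatively". Section IV.C gives the reason for the window: "We chose to intervene at 6-12 months postoperatively because the first year after surgery represents the most rapid phase of weight loss". It adds that prolonging this phase may improve long-term results.

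Two other sections describe the expected course. Section IV.B takes expected loss at the three entry times from an adolescent surgical cohort, "defined as a \geq 26%, \geq 28%, and \geq 31% decrease in weight, respectively, from preoperative weight". Section II places the peak of weight loss at about one year and sketches the rest of the course in these words: "with the most rapid loss within the first 6 months) followed by modest weight regain". It also says that loss at 6 months is close to loss at 3 years.

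Section IV.B describes allocation as 1:1, seven per arm and double-blind. It names no stratification, blocking or minimisation. Under Planned analyses in section IV.F, means and variability of the Aim 2 and 3 outcomes will be "graphically presented and visually compared for experimental vs. control groups", because these aims are not powered for inference. The only split announced for the efficacy measures, in section IV.E, is by reason for eligibility: inadequate loss versus remaining severe obesity.

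**The concern.** A participant entering at 6 or 9 months is followed through a period in which further loss is expected without drug. One entering at 12 months is followed through months 12 to 15, after the stated maximum. Entry time is therefore a prognostic factor for the Aim 2 outcome, and it is known at screening.

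With seven per arm, the arms can easily differ by one or two 12-month entrants. The raw difference in mean percent change then moves for a reason unrelated to drug, and a plot by arm alone would not show it. The pooled mean also combines added loss within the first year with avoidance of regain after it, and the pooled spread includes variation due only to timing.

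**Working it through.** The plan gives no figure for the weight contrast, so there is none to reproduce. Change is taken relative to weight at entry, which Aim 2 implies but does not state.

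**1. Expected 12-week change without drug** (section IV.B losses of 26%, 28% and 31%, so remaining weight is 74%, 72% and 69% of preoperative weight)
- 6-month entry: 72/74 - 1 = -2.7%.
- 9-month entry: 69/72 - 1 = -4.2%.
- 12-month entry: no figure. If loss at 3 years is again about 26% (section II), weight rises from 69% to 74% over 24 months: 74/69 - 1 = +7.2%. Spread evenly over eight 3-month periods, this is +0.9% each. Even regain is an assumption, so I use the range 0 to +0.9%.

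**2. Chance imbalance between arms**

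The mix of entry times is not given. Assume 5/5/4 at 6/9/12 months. For a random 7/7 split of 14 fixed values, the SD of the arm difference is sqrt(S² × 2/7), where S² is the variance of the 14 expected changes (divisor 13).
- 12-month change 0: S² = 3.00, SD = sqrt(3.00 × 2/7) = 0.93 points.
- 12-month change +0.9%: S² = 4.54, SD = sqrt(4.54 × 2/7) = 1.14 points.

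Enumerating all 3,432 splits, the spurious difference exceeds 1 point in 20% of them (change 0) and 44% (+0.9%). With four 12-month entrants, the chance of an even 2/2 split is 6 × 252/3,432 = 44%. In the other 56% the arms differ by two or more. A difference of two, offset by 9-month entrants, shifts the contrast by 2 × 4.17/7 = 1.2 points; offset by 6-month entrants, by 2 × 2.70/7 = 0.8.

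**3. Sensitivity** (12-month change 0 to +0.9%)

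| Assumption | SD of arm difference | Share of splits above 1 point |
|---|---|---|
| 5/5/4, cohort course | 0.9 to 1.1 | 20% to 44% |
| 5/5/4, loss half as steep at 6 and 9 months | 0.5 to 0.7 | 4% to 8% |
| 9/3/2, cohort course | 0.7 to 0.8 | 7% to 29% |

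**4. Size against ordinary noise**

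The documents give no SD for 12-week change. Adding S² to an assumed variance among participants with the same entry time:
- SD 5: the standard error of the arm difference is sqrt((25 + 3.00 to 4.54) × 2/7) = 2.8 to 2.9, against 2.7 without the entry-time part.
- SD 3: sqrt((9 + 3.00 to 4.54) × 2/7) = 1.9 to 2.0, against 1.6.

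**5. Is a two-level factor enough?**

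Merging 6 and 9 months leaves variance (10/14) × (1.46/2)² = 0.38. The total between entry times is 2.79 to 4.22 (divisor 14). The split at 12 months therefore captures 86% to 91% of it.

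**The case against.** Much of the opposing case stands.

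- **The inputs are soft.** The 26/28/31% values are cohort values used as eligibility thresholds, and participants admitted for inadequate loss fall below them. A reader might infer that 9- and 12-month entrants differ by at least 4.2 points without drug. The documents do not support that as a lower bound, since enrolled patients may follow a flatter course. Regain of 2% in 3 months would enlarge every figure, but it is more than twice what section II implies.
- **It is chance error, not bias.** Randomisation ensures this. Nor does it dominate: ordinary variation between participants is probably larger (step 4).
- **No decision rests on it.** A reader might infer that the weight contrast will be carried into the larger trial as its planning effect. Section IV.F instead assigns that role to the feasibility estimates and withholds inference for Aims 2 and 3.
- **Silence is not proof.** Figure 1 and the text of footnote a, attached to the entry window, are not available. Either could carry allocation detail.
- **Clinic contact is a weak argument.** The visit section says "For those with a screening/enrollment visit at 12 months, Visit 4 will typically not be concurrent with a regularly scheduled postop visit". A reader might infer poorer weight data for these entrants, but all participants have the same study visits with weight measured.
- **Other factors compete.** Section III shows that outcome also varies by procedure, and 14 people cannot be stratified on everything.

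What remains is that a descriptive comparison by eye gives the reader no means of telling a timing imbalance from a drug effect. Entry time is also the factor for which the protocol itself supplies expected values over almost exactly the follow-up period.

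**Conclusion.** The point holds as a modest, inexpensive improvement. On the protocol's own values, the expected untreated change is about -2.7% for 6-month entry and -4.2% for 9-month entry. It is about zero or a modest gain for 12-month entry, where the value is partly assumed. Neither the readable allocation text nor the weight comparison uses entry time.

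Under an assumed 5/5/4 mix, the resulting chance error in the arm difference has an SD of about 0.9 to 1.1 points at seven per arm. It falls to about 0.5 to 0.7 if courses are half as steep, and is about 0.7 to 0.8 under a 9/3/2 mix. The result depends on the assumed mix, on even regain after month 12, and on weight at entry as the baseline. It affects how Aim 2 (and fat mass in Aim 3) can be read. Aim 1 and the sample size justification are untouched. Nothing here says which entry window is right.

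**What to change.** **Reporting, whatever the state of enrolment.** For percent weight change, and for fat mass in Aim 3:
- mark each participant's months since surgery on the plots already planned;
- tabulate change by arm within entry window (6-9 versus 12 months);
- give the between-arm difference averaged over entry windows beside the raw one, using only windows in which both arms have participants.

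**Allocation, only for participants not yet randomised.** Stratify in small permuted blocks, or minimise, on the same two-level factor. Section III speaks of study start in the past tense, so this part may come too late for some or all. If Figure 1 or footnote a already specifies it, say so in the text of section IV.B.

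**Cost.** One line in the analysis plan and, where still possible, one in the randomisation set-up. No new data are needed. The within-window figures will rest on very few people, perhaps two per arm at 12 months, and should be labelled as descriptive. Incomplete blocks may give 8/6 instead of 7/7.

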Nausea, Vomiting, Diarrhea	DSMP				
Rare, but Serious ⁴⁰					

Acute myopia, Secondary angle closure glaucoma	DSMP
Oligohidrosis, Hyperthermia	DSMP (including temperature at every study visit)
Metabolic acidosis	Bicarbonate at enrollment, visit 2, and visit 4
Suicidal ideation/attempt	DSMP with assessment at every study visit
Fetal toxicity	Pregnancy tests at enrollment and every study visit
(Pregnancy Risk Factor Category D- positive evidence of risk)	Requirement for females to either have a LARC (majority) or documented commitment to use 2 forms of birth control
Withdrawal symptoms	Gradual discontinuation at the end of the study
Hyperammonemia and encephalopathy	Drug interaction check; DSMP
Kidney stones	BMP at enrollment, visit 2, and visit 4; Drug interaction check; DSMP
Topiramate-Ethanol interaction (potential to cause increased CNS depression)	Counseling about alcohol avoidance, and specific language about this risk in the consent/assent

Methods for systematically assessing changes in mood, suicidality, and cognition.

Mood:

Changes in mood will be systematically screened for using the Center for Epidemiologic Studies Depression Scale (CES-D). This is a 20-item self-report questionnaire that covers areas including depressed mood, feelings of guilt/worthlessness, helplessness, psychomotor retardation, loss of appetite and sleep disturbance over the previous week. ⁴⁶ This instrument has yielded adequate internal reliability that is robust to age, clinical vs. nonclinical setting, and risk of bias. ⁴⁷ The original version of the measure is appropriate for individuals 12 years of age and older. The CES-D is routinely administered to individuals receiving care at the Children's Colorado Bariatric Surgery Center at every follow-up pre-operative and post-operative clinic appointment.

The proposed study will additionally administer the CES-D at all study visits not aligned with a clinical visit and will be scored by the PI or professional research assistant. A CES-D score <20 indicates no to mild depressive symptoms. And a CES-D score ≥20 indicates elevated depressive symptoms. This is based on a metaregression that supported higher cut points having better diagnostic accuracy.⁴⁷

Any study participant who a) newly scores ≥20 at any time during the study or b) has a baseline score of ≥20 and who demonstrates any absolute increase in this score, compared to previous measures, will be discussed within 72 hours with the Bariatric Surgery Center's pediatric clinical psychologist to consider a more comprehensive follow-up clinical interview. The clinical interview will guide additional management recommendations, which may include psychoeducation on depression, a referral to therapy, a referral to psychiatry, and/or a reduction of study medication.

Weekly phone calls after study drug start also include a question about depressed mood over the previous week and if present, ask participants to rank this as mild, moderate, or severe. If depressed mood is present and moderate or severe, the PI will discuss follow-up steps with the participant and caregiver within 24 hours of identification after consulting with study psychologist [name]; If mild and new, the PI will discuss with study psychologist [name] within 1 week of identification.

Suicidality:

Suicidal ideation and behavior will be assessed using the Columbia Suicide Severity Rating Scale (C-SSRS)^{48,49} at enrollment and each study visit. Any participant who reports suicidal behavior or suicidal ideation with some intent to act (Type 4) or with intent and a specific plan (Type 5) during the study will be discussed with the PI during *that visit*. The PI will determine whether the participant should be escorted to the Children's Hospital Colorado Emergency Department for an emergent mental health evaluation or will be discussed within 72 hours with the Bariatric Surgery Center's pediatric clinical psychologist for additional assessment/treatment recommendations.

For both mood and suicidality, if a participant's psychiatric disorder can be adequately treated with psycho- and/or pharmacotherapy, then the patient, at the discretion of the mental health provider, should be continued in the trial on randomized therapy.

Cognition:

At 1, 2, and 3 weeks after study medication initiation, weekly during any additional titration during the protocol, and at each study visit, participants will be asked to complete a self-report checklist of possible adverse effects that have reported associations with the active study drugs, which include changes in memory, attention/concentration, word-finding/language, and overall academic/job performance, along with the perceived severity of each (mild, moderate, or severe).

Severe cognitive difficulty, which is a drug dose reduction/discontinuation criteria, will be defined as self-report of a "severe" change in memory, attention/concentration, or word finding/language that the participant believes is significantly impacting academic or job performance and that is not otherwise explained by non-study medication related factors.

Of note, in the one randomized controlled trial of topiramate for weight loss among severely obese adolescents⁵⁰ (24-week intervention of 75mg/day topiramate vs. placebo), Fox et al. found no significant differences between topiramate and placebo groups on subscales of the Cambridge Neuropsychological Test Automated Battery (CANTAB) or Behavioral Rating Inventory of Executive Function-Self Report (BRIEF-SR), and on the Connors Continuous Performance Test II (CPT II), the only significant finding was faster reaction time in the topiramate group compared to the placebo group.

2) Data and Safety Monitoring Plan (DSMP):

Definitions: The PI will use the FDA's/Center for Drug Evaluation and Research's "Guidance for Industry Investigators Safety Reporting Requirements for INDs and BA/BE Studies" document to define the terms: adverse event (AE), suspected adverse reaction, adverse reaction, unexpected, serious, and life-threatening.

1. Describe who will monitor for unanticipated problems of subjects: The PI and the professional research assistant (who reports directly to the PI) will primarily monitor for unanticipated events (e.g. breach of confidentiality) and unexpected adverse events. Additionally, a Safety Officer will be appointed to this study to objectively oversee unanticipated problems. We define an unexpected AE (21 CFR 312.32(a)) as an adverse event or suspected adverse reaction that is not listed in the FDA-approved label or is not listed at the specificity or severity that has been observed. Unexpected also refers to AEs or suspected adverse reactions that are mentioned as occurring with a class of drugs or as anticipated from the pharmacological properties of the drug, but are not specifically mentioned as occurring with phentermine or

immediate release topiramate. All unanticipated problems will be reported to COMIRB within 5 days of the occurrence.

2. Will the PI be responsible for ongoing review of local adverse events and serious adverse events? (physical or psychological harm to subjects): Yes. The PI will be responsible for ongoing review of local AEs and serious adverse events (SAE).

We define an AE **(21 CFR 312.32(a))** as any untoward medical occurrence associated with the use of the study drugs, whether or not considered drug related. This may be any unfavorable or unintended sign (e.g. abnormal lab), symptom, or disease temporally associated with the use of a drug, and does not imply any judgment about causality.

We define an SAE **(21 CFR 312.32(a))** as an adverse event or suspected adverse reaction that results in any of the following: death, life-threatening adverse event, inpatient hospitalization or prolongation of existing hospitalization, a persistent or significant incapacity or substantial disruption of the ability to conduct normal life functions, or a congenital anomaly/birth defect. Other events could be considered serious if they may jeopardize the subject and may require medical or surgical intervention to prevent one of the above listed outcomes (e.g. allergic bronchospasm requiring intensive treatment).

Specifically, an AE form will be completed for any complaints/AEs that are participant-reported or elicited during the study. And an SAE report will be generated if criteria are met. AEs will be identified with the following procedures:

- -Comprehensive review of systems at every study visit (to capture possible AEs not reported previously)
- -Physical exam at every study visit (e.g. new murmurs, rubs, or gallops, new increased work of breathing, new pulmonary edema, new peripheral edema);
- -Vitals at every study visit (e.g. new fever, tachycardia, new elevated blood pressure/hypertension)
- -Phone call 1, 2, and 3 weeks after study drug initiation and in-person with a questionnaire at visits 2, 3, and 4 to review known possible side effects of phentermine and topiramate
- -Lab monitoring: basic metabolic panel (to assess for new metabolic acidosis: bicarb < 18 mmol/L); urine pregnancy tests for all females at every visit.
- -Monitoring of mood, suicidality, and cognition per above with validated assessments at enrollment and every study visit (e.g. new or worsened depression, new suicidal ideation/behavior)
- -Between study visits, participants with questions about symptoms will also be encouraged to call the PI directly (voicemail messages are forwarded to the PI's password-protected email)
- 3. To what external entities will local adverse events be reported?: In addition to COMIRB, the PI will report local adverse events to the FDA, according to their safety reporting requirements: https://www.fda.gov/downloads/Drugs/Guidances/UCM227351.pdf). Specifically, the PI will report to the Division of Metabolism and Endocrinology within the FDA's Center for Drug Evaluation and Research, which reviewed the IND application for this study. The PI will report to this Division: 1) Any unexpected fatal or life-threatening suspected adverse reactions no later than 7 calendar days after initial receipt of the information, and 2) Any a) serious, unexpected suspected adverse reactions, b) findings from other clinical/animal/in-vitro studies

that suggest significant human risk, and c) a clinically important increase in the rate of serious suspected adverse reactions no later than 15 calendar days after determining that this information qualifies for reporting.

4. Will periodic global review of safety/adverse events (serious adverse events and adverse events) occur?: Yes, reviews will be performed by the PI, and a three-member data and safety monitoring board (DSMB), including a primary Safety Officer.

Reviewer	Expertise	Review Frequency	Written Reports	Report Frequency
PI	Board Certified in Internal Medicine and Pediatrics; Assistant Professor in Pediatrics, Section of Nutrition with specialized training in pediatric anti-obesity pharmacotherapy; Primary author of Children's Hospital Colorado's Lifestyle Medicine clinical protocols for anti-obesity pharmacotherapy.	Monthly	Yes	Within 5 days of any SAE and monthly for all other AEs
Medical/Safety Officer	Endocrinology faculty member with expertise in pediatric clinical trials	Every 3 months	Yes	Every 6 months
Data and Safety Monitoring Board (DSMB)	Safety Officer (above) + 2 additional faculty with clinical and clinical trial expertise in using anti-obesity pharmacotherapy across the age range studied	Every 6 months	Yes	Every 6 months

A three-member Data and Safety Monitoring board, including a primary Safety Officer, who are independent of the study personnel, have been appointed to this study. Like the study staff, they will be blinded to participants' randomized treatment assignments.

The Safety Officer will:

- 1) Approve criteria for modifying or discontinuing study drugs for individual participants
- 2) Review data generated by the study, including study safety events (SAEs) every 3 months for the duration of the study.

The three-member Data and Safety Monitoring Board will:

- 1) Evaluate the progress of the trial, including periodic assessments of recruitment, screen failures, enrollment, and retention
- 2) Report on the safety and progress of the study every 6 months
- 3) Consider the impact of new or relevant information such as scientific or therapeutic developments (provided by the PI) that may have an impact on the safety or scientific integrity of the study.
- 4) Determine whether the overall integrity and conduct of the study remain acceptable

- 5) Based on these responsibilities/functions, the DSMB will act in an advisory capacity and recommend one of the following actions to the PI ([name]) every 6 months:
 - A) Continue the study according to the protocol and any related amendments.
 - B) Modify the study protocol. Modifications may include, but are not limited to, changes in inclusion/exclusion criteria, frequency/mechanism of safety monitoring, alterations in study procedures, and changes in duration of observation and follow-up.
 - C) Discontinue the study (with provisions for organized discontinuation in accordance with safe medical practice).
- **5. Will any formal interim analysis be performed?:** Interim assessments of feasibility, acceptability, and safety per above will be performed, but there will be no formal interim analysis for this 12-month study.
- **6. Are there defined** participant **discontinuation criteria?**: There are no *participant* discontinuation criteria. However, there are defined *drug* discontinuation criteria as follows:
 - a) Development of an anaphylactic allergic reaction, pulmonary hypertension, evidence of new valvular heart disease, uncontrolled systemic hypertension, new arrhythmia (including persistent tachycardia), severe anxiety unresponsive to dose decrease, psychiatric disorder that cannot be adequately treated with psycho- and/or pharmacotherapy at the discretion of the study's clinical psychologist, serotonin syndrome, or pregnancy during the pharmacotherapy intervention will lead to discontinuation of phentermine.
 - b) Development of an anaphylactic allergic reaction, nephrolithiasis, severe, persistent cognitive difficulties, psychiatric disorder that cannot be adequately treated with psychoand/or pharmacotherapy at the discretion of the study's clinical psychologist, new acute myopia or secondary angle closure glaucoma, severe metabolic acidosis, hyperammonemia with encephalopathy, or pregnancy during the pharmacotherapy intervention will lead to discontinuation of topiramate.
 - c) If one medication is stopped secondary to the criteria above, the participant, if in agreement, will be continued on the other medication as monotherapy.
 - d) With consent, participants for whom one or both medications are stopped will continue to be followed according to the proposed study timeline.

7. How will the PI/research team determine if an adverse event (AE) is related to either of the study drugs?

Relatedness will be defined according to the National Institutes of Health National Institute on Aging Data Safety and Monitoring Plan Toolkit template (https://www.nia.nih.gov/research/dgcg/clinical-research-study-investigators-toolbox/data-and-safety-monitoring) as follows:

- **Definitely Related**: The AE is clearly related to the study drug i.e. an event that follows a reasonable temporal sequence from administration, follows a known or expected response pattern to the drug (intervention), that is confirmed by improvement on stopping and reappearance of the event on repeated exposure and that could not be reasonably explained by the known characteristics of the subject's clinical state.
- Possibly Related: An AE that follows a reasonable temporal sequence from administration of the study drug (intervention), follows a known or expected response pattern to the intervention, but that could readily have been produced by a number of other factors.
- **Not Related**: The AE is clearly not related to the drug i.e. another cause of the event is most plausible; and/or a clinically plausible temporal sequence is inconsistent with the

onset of the event and the study intervention and/or causal relationship is considered biologically implausible.

8. Are there overall protocol/study stopping rules?: Any life-threatening adverse drug experience (other than an anaphylactic reaction), or death of any patient, determined to be associated with either study drug.

2) Data collection tools

- Primary Aim 1: Questionnaires. We believe these represent a minimal risk to participants. The only potential study-related burden for these tools is the time required to complete them, which we have factored into our determination for incentives. These are essential to adequately address Aim 1.
- Secondary Aim 2: Weight. Measuring weight is a standardized part of every primary care
 and most specialty care medical visits throughout the lifespan. We believe this represents
 minimal risk to participants. In the perioperative setting for adolescent bariatric surgery,
 patients have the option to decline being informed of their weight if this increases stress,
 anxiety, or other emotional discomfort. Change in weight is the central physiologic measure
 of interest for this study to assess initial efficacy of the medication vs. placebo group.
- Secondary Aim 3: Venipuncture for bloodwork, manual blood pressure, DEXA, indirect calorimetry, and questionnaires.
 - We believe the manual blood pressure and questionnaires (routine components of most medical visits) both represent minimal risk.
